6. ANALYSIS SETS

6.1 Full Analysis Set

For cohorts 1-4, the full analysis set includes all enrolled subjects who are randomized. For cohorts 1b, 3b, and 4b, the full analysis set includes all subjects who sign the informed consent form and receive at least one dose of investigational product.

Disposition data will be summarized and listed using the Full Analysis Set.

6.2 Safety Analysis Set

This analysis set includes all enrolled subjects who receive at least one dose of active drug or placebo.

All safety, treatment exposure, demographic and baseline characteristic data, and efficacy data will be summarized and listed using the Safety Analysis Set. The Safety Analysis Set will be analyzed as treated.

6.3 Pharmacokinetic (PK) Analysis Set

This analysis set includes all subjects who receive at least one dose of active study treatment and have sufficient plasma concentration data to characterize PK profile. Subjects may be excluded if they have protocol deviations which would affect the PK results.

7. PLANNED ANALYSES

7.1 Interim Analysis and Early Stopping Guidelines

An external independent DSC will formally review the accumulating data from this study. Analyses for the DSC are provided by the Independent Biostatistical Center (IBC), which is external to Arrowhead.

7.2 Final Analysis

Final Analysis will be performed upon completion of all cohorts in the study, following database lock and unblinding.

8. DATA SCREENING AND ACCEPTANCE

8.1 General Principles

The objective of data screening is to assess the quantity, quality and statistical characteristics of the data related to the requirements of the planned analyses.

8.2 Data Handling and Electronic Transfer of Data

Arrowhead Pharmaceutical Inc. (Arrowhead) Data Management will provide all data to be used in the planned analyses. This study will use the RAVE database.

All data collected in the eCRF will be extracted from RAVE. Protocol deviations will be transferred from the Clinical Trial Management System. Unblinded randomization list will be transferred from Novotech to Arrowhead Statistical Programming (or a CRO delegate) upon Database Lock (DBL).

Data will be provided to EMB as Standard Data Tabulation Model (SDTM) datasets.

8.3 Handling of Missing and Incomplete Data

Missing dates will not be imputed, except in the case of determining treatment-emergent status for AEs, concomitant status for medication and procedures, and for missing or partial dates where a complete date is required for calculations.

Missing	Imputation	Exception
Day	01	Default to Study Day 1 if an AE, medication/procedure starts the same year and month as Study Day 1 and the end date has same year and month as Study Day 1 or later.
Day / Month	01 / Jan	Default to Study Day 1 if an AE, medication/procedure starts the same year as Study Day 1 and the end date has same year as Study Day 1 or later.
Day / Month / Year	
To calculate a missing start date:
 
 1. If a partial or complete stop date is present: 
 a. Stop date < first dosing date: impute January 1 of the stop year b. Stop date \geq first dosing date: impute the date of first dose 2. If it is unknown whether the stop date is < or \geq first dosing date due to a missing or partial stop date, or if a stop date is not collected: impute date of first dose. 	

Medications and procedures with missing or partial end dates will be assumed to be concomitant unless a partial end date documents it as ending prior to treatment.

The original missing or partial date, the imputed complete date, and an indicator variable that indicates which dates were imputed will be retained in the database. Dates will be presented as collected in all listings. Imputed dates will not be presented in listings but may be used for summary tables.

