# 11.3 Timing, Frequency, and Method of Detecting AEs

Any pre-existing conditions or signs and/or symptoms present in a participant prior to the start of the study (i.e., before informed consent) should be recorded as Medical/Surgical History.

All AEs occurring after informed consent and on or before the final visit must be reported as AEs; only AEs that occur post-dose will be considered treatment-emergent. All AEs must be recorded irrespective of whether they are considered drug-related. AEs will be collected through the EOS or through 30 days after the last dose whichever is longer.

At each visit/assessment in the period defined above, AEs will be evaluated by the PI (or medically qualified designee) and recorded.

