5. DEFINITIONS

Day 1:

For each subject, Day 1 is defined as the first day that protocol-specified study treatment is administered to the subject.

End of Study (EOS) Date:

For each subject, the EOS date is the study completion/early termination date recorded on the eCRF.

Study Day:

For each subject, and for a given date of interest, study day is defined as the number of days relative to Day 1:

- After first dose date: study day = date of interest – Day 1 date + 1
- Prior to first dose date: study day = date of interest – Day 1 date, so that the day prior to Day 1 is Day -1

Study End Date:

The study end date is when the last subject finishes the EOS visit.

Baseline Values:

For all variables, baseline is defined as the last non-missing value obtained prior to the first dose administration on Day 1.

For ECG, if a triplicate is taken prior to the first dose administered on Day 1, baseline is defined as the mean over the set of triplicate assessments.

Analysis Day:

Selected endpoints will be summarized based on Analysis Day defined using Study Day as below.

Scheduled Visit/ Analysis Day	Day 8	Day 15	Day 29	Day 43	Day 57	Day 71	Day 85	Day 99	Day 113
Study Day Window Cohort 1-4	[6,10]	[13,17]	[27,31]	[41, 45]	[55,59]	[69,73]	[83,87]	[97,101]	[111,115]
Study Day Window Cohort 1b,3b,4b	NA	[13,17]	[27,31]	NA	[55,59]	[66,76]	[83,87]	NA	[108,118]

If there is more than one record in a study day window, the analytical record for that specific analysis day will be defined as the record closest to the scheduled visit day. If two records are equidistant from the scheduled visit day, then the earlier record will be chosen. If there are multiple records on the same day, the last record will be used.

Duration of study:

EOS date – Day 1 date + 1

Treatment-Emergent Adverse Event (TEAE):

TEAEs are defined as adverse events occurring on or after the first dose of study treatment through EOS or pre-treatment existing conditions that worsen after the investigational product administration.

Treatment-emergent SAEs (TESAEs):

TESAEs are defined as serious adverse events occurring on or after the first dose of study treatment through EOS or pre-treatment existing conditions that worsen after the investigational product administration.

TEAE at Injection Site:

TEAE occur at the injection site. MedDRA Preferred Terms which are included in LISR are listed in Protocol Section 16.2.

TEAE Related to Local Injection Site Reaction (LISR):

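### The partial-start-date rule in SAP 8.3 can move an adverse event to Day 1 although its recorded stop date is before dosing, and so count it as treatment-emergent

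*SAP*

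**What the plan says.** SAP 8.3 leaves missing dates unimputed "except in the case of determining treatment-emergent status for AEs" and for a few other listed uses. Its table has three rows for start dates:

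- **Day missing.** Use the first of the month, with the exception "Default to Study Day 1 if an AE, medication/procedure starts the same year and month as Study Day 1". This exception carries a second condition, on when the event stopped: "the end date has same year and month as Study Day 1 or later".
- **Day and month missing.** Use 1 January, with the same exception tested on the year alone: "the end date has same year as Study Day 1 or later".
- **Everything missing.** Compare the stop date with the first dose: "Stop date < first dosing date: impute January 1 of the stop year". A stop on or after first dosing gives the date of first dose.

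The section adds: "Imputed dates will not be presented in listings but may be used for summary tables".

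SAP section 5 turns the imputed start into a classification: "TEAEs are defined as adverse events occurring on or after the first dose of study treatment through EOS". Protocol 11.3 says "only AEs that occur post-dose will be considered treatment-emergent".

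**The concern.** In the first two rows, sharing Day 1's month (or year) is enough to satisfy the end-date test. An event with a complete stop date before Day 1, but in the same month or year, therefore passes. It receives a start later than its own stop and is tabulated as treatment-emergent, although the record shows that it was over before any drug was given.

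Such events can occur. Protocol section 11 has AEs recorded from consent, and the schedules allow screening from Day -45 in healthy volunteers and Day -60 in patients. Nothing else in the SAP overrides the rule for AEs: the sentence in 8.3 about partial end dates that show an end before treatment covers only medications and procedures. The second part of the TEAE definition, worsening of a pre-existing condition, does not cover an event that resolved before dosing.

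At stake are the all-TEAE counts in SAP 9.6.1 (overview, SOC/PT and severity tables) in very small groups. The tables would also disagree with the listings, which show dates as collected.

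**Working it through.** The plan states no figure to reproduce, so the check applies the rule literally.

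**Worked cases.** The dates are illustrative, with Day 1 = 20 March 2021.

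| Recorded start | Recorded stop | Start under SAP 8.3 | TEAE? | Start under the fix |
|---|---|---|---|---|
| March 2021, day unknown | 12 March | 20 March (20 − 12 = 8 days after stop) | yes | 1 March, not a TEAE |
| 2021 only | 10 February | 20 March (18 + 20 = 38 days after stop) | yes | 1 January, not a TEAE |
| Wholly missing | 12 March | 1 January | no | row unchanged |
| February 2021, day unknown | 25 February | 1 February | no | unchanged |
| March 2021, day unknown | 25 March | 20 March | yes | unchanged |

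Rows 1 and 3 describe the same event. With less start information, the SAP classifies it correctly. Row 4 shows that the rule works when the stop falls in an earlier month.

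**How often the rule fails, given such a record.** Take every Day 1 in 2021 and every start/stop pair lying wholly before it in a screening window of L days, all pairs weighted equally. The year and the weighting are assumptions. Each Day 1 has L(L+1)/2 pairs: 1,035 for L = 45 and 1,830 for L = 60.

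- *Day missing.* The rule fails when start and stop both fall in Day 1's month. For Day 1 on day d of the month that is d(d−1)/2 pairs. Summed over a month these give 4,960 (31 days), 4,495 (30 days) or 3,654 (28 days). Over the year: 7 × 4,960 + 4 × 4,495 + 3,654 = 56,354. Shares: 56,354 / (365 × 1,035) = 14.9%, and 56,354 / (365 × 1,830) = 8.4%.
- *Day and month missing.* The rule fails when both fall in Day 1's year. For L = 45: (15,180 + 320 × 1,035) / 377,775 = 91.7%. For L = 60: (35,990 + 305 × 1,830) / 667,950 = 88.9%. The first term in each numerator covers Day 1 dates too early in the year for a full window.

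These are shares of pre-dose AEs that already have that kind of partial start date. They are not shares of all AEs. Under the fix all four fall to zero.

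**Effect of one false case on incidence.** Group sizes come from the cohort tables and SAP 9.1, which pools placebo across cohorts (4 × 4 = 16).

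- 4 active volunteers: 1/4 = 25 points.
- 6 patients: 1/6 = 16.7 points. With the two extra patients that the protocol synopsis allows, 1/8 = 12.5 points.
- 16 pooled placebo: 1/16 = 6.25 points.

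These are maxima. Overall TEAE incidence moves only if the subject has no other TEAE, and a SOC or PT row only if there is no other in that category. Event counts rise by one in every case.

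**The case against.** **The records will be rare.** This stands. Conditions that predate consent go to medical history (Protocol 11.3), so a screening AE lies between a recorded consent date and Day 1, and the synopsis asks for AE reporting within about 48 hours. A known stop with only a start year is close to theoretical in that setting. The day-missing case also needs onset and stop in Day 1's own month, which excludes much of the window. The screening biopsy adds little, because the procedure date would usually fix the onset of an event it caused.

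**The primary endpoint is affected.** A reader might infer this, but the documents do not support it. The endpoint counts events possibly or probably related to treatment, and Protocol 11.5.3 makes occurrence before administration a ground for judging an event not related. That largely protects it.

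**The table contradicts itself.** A reader might also infer this, but it goes too far. Each row governs a different pattern of missingness and no record falls under two rows. The rows are inconsistent in the comparison they make.

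**Imputing toward treatment is conservative.** That is sound when timing is unknown. Here the recorded stop date settles it.

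**Checks would catch it.** Original dates and an imputation flag are retained, and programs are independently validated (SAP 8.7). A start after its stop is detectable, but validating a program against this rule would confirm the wrong result.

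**The wording could mean an end on or after Day 1.** The text makes a shared month, or a shared year, sufficient in itself, so the gap remains.

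**Conclusion.** The rule is wrong as written. In the day-missing and day-and-month-missing rows, an AE with a recorded stop before Day 1 in the same month (or year) is given a start after its own stop and classed as a TEAE, contrary to Protocol 11.3.

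The practical effect is probably small and cannot be sized from the documents, which do not say how many such records exist. It falls mainly on all-TEAE summaries in a descriptive study with no formal hypotheses. Medications and procedures share the wording, but SAP 9.6.9 sets concomitant status by end date, so the effect is mainly on AEs. The point is worth correcting before database lock because the error is certain when the pattern occurs and the remedy is almost free. It does not call the study's conclusions into question.

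One assumption matters. The two rows do not say what happens when the end date is missing or the event is ongoing. The check treated such events as meeting the end-date condition, and the fix makes that explicit.

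**What to change.** In both rows keep the existing start condition (same year and month, or same year, as Study Day 1). Replace only the end-date condition with:

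*and the stop date is on or after Study Day 1, is missing or ongoing, or is partial and cannot be shown to be before Study Day 1.*

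Otherwise use the row's standard imputation (01, or 01/Jan), so that an event with a stop before Day 1 is not treatment-emergent.

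Two variants should be avoided:

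- **Dropping the start condition.** With Day 1 on 20 March, an event starting in February (day unknown) and stopping on 25 March would move to Day 1, although its onset is known to be before dosing.
- **Flooring the imputed start at the consent date.** A medication started in March (day unknown) and stopped on 5 March, with consent on 10 March, would get a start of 10 March, again after its stop.

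The cost is one sentence of SAP text, used in two rows, and a trivial program change. No data collection changes. In the cases checked with a stop on or after Day 1, or missing, the imputed start was the same as before.

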8.4 Detection of Bias

Lack of protocol compliance may introduce potential bias in the estimation of protocol endpoints. Clinical study team will assess incidence of important protocol deviation. Clinical study team will also identify and document the criteria for important protocol deviations.

8.5 Outliers

Descriptive statistics may be used to identify outliers of key variables. However, no statistical analysis or adjustment for outliers is planned; outliers will not be omitted from summaries.

8.6 Distributional Characteristics

Distributional assumptions for the secondary endpoints may be assessed. Prior to implementation of parametric methods of analysis, if the assumptions of the analysis are not met, then alternative methods may be utilized. The use of alternative methods will be fully justified in the CSR.

8.7 Validation of Statistical Analyses

All computations for statistical analyses will be performed using SAS® software Version 9.4 or later. All SAS programs used in the production of statistical summary outputs will be validated with independent programming prior to finalization. In addition, all program outputs will be independently reviewed. The validation process will be used to confirm that all data manipulations and calculations were accurately done. Once validation is complete, a statistical reviewer will perform a final review of the documents to ensure the accuracy and consistency with this plan and consistency within tables. Upon completion of validation and quality review procedures, all documentation will be collected and filed by the project statistician or designee.

9. STATISTICAL METHODS OF ANALYSIS

9.1 General Considerations

Descriptive statistics will be provided for selected demographic, safety and efficacy data. Descriptive statistics on continuous data will include the number of subjects, mean, median, standard deviation, minimum & maximum while categorical data will be summarized using frequency counts and percentages. Graphical summaries of the data may be also presented.

Unless otherwise noted, all summaries and figures will be presented by treatment, with NHV Cohorts 1-4 and Patient Cohorts 2b, 3b, and 4b presented separately. Subjects receiving placebo will be pooled across cohorts.

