#### Reference Formulation:

The reference formulation is placebo (PBO): normal saline (0.9%) administered subcutaneously, volume matched to the corresponding ARO-HSD dose volume.

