#### (Patient cohorts 1b, 3band 4b)

- Change in ALT and in AST as a marker of ARO-HSD activity compared to baseline
- Change in cytokeratin-18 compared to baseline
- Change in IL-1 $\beta$ , IL-6, IL-10, INF-gamma, and TNF- $\alpha$  compared to baseline
- Change in retinol and retinol binding protein compared to baseline
- Change in liver fat using MRI-PDFF compared to baseline
- Change in blood exosomal HSD17β13 mRNA levels (if feasible) compared to baseline
- Change in blood exosomal PNPLA3 mRNA levels (if feasible) compared to baseline
- Change in Enhanced Liver Fibrosis (ELF) Score at EOS compared to baseline
- Change in Pro-C3 at EOS compared to baseline
- Liver biopsy derived HSD17β13 mRNA expression compared to baseline
- Liver biopsy derived HSD17β13 protein expression compared to baseline in response to multiple doses of ARO-HSD (if scientifically feasible)
- Liver biopsy derived change in PNPLA3 mRNA expression compared to baseline
- Liver biopsy derived change in PNPLA3 protein expression compared to baseline in response to multiple doses of ARO-HSD (if scientifically feasible)

**Study Population/Patient Number:** This study will be conducted in adult males and females, aged 18 through 65 years (minimum of 19 years of age for NASH or suspected NASH patients) with BMI between 18.0 and 40.0 kg/m^2 enrolled and dosed as follows (see also Cohort Summary below):

NHV Cohorts 1, 2, 3, and 4: Each double-blind cohort will enroll eight (8) subjects (4 active: 4 PBO) with all cohorts planned to receive single escalating doses of ARO-HSD or placebo at dose levels of 25 mg (Cohort 1), 50 mg (Cohort 2),  $\leq$  100 mg (Cohort 3), and  $\leq$  200 mg (Cohort 4). These dose levels represent the highest dose that may be used in the cohort but after Cohort 1, the Data Safety Committee (DSC) may adjust the dose lower if indicated.

• Patient Cohorts 1b, 3band 4b: All patients will have suspected NASH and meet patient entry criteria. Cohorts are open label with up to 6 patients per cohort. All subjects will receive two doses of ARO-HSD at dose levels of 25 mg (Cohort 1b), ≤ 100 mg (Cohort 3b) and ≤ 200 mg (Cohort 4b). These dose levels represent the highest dose that may be used in the cohort but after Cohort 1, the DSC may adjust the dose lower if indicated.

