### Supply, Preparation, Storage, and Labelling of ARO-HSD

ARO-HSD will be supplied as a sterile Type-1 glass 2.0-mL vial (1.2 mL nominal volume, 1.0 mL withdrawable volume).

Strength: 200 mg/mL Volume: 1.0 mL

Appearance: Clear, colorless to yellow solution

Inactive ingredients: 0.5 mM sodium phosphate monobasic, 0.5 mM sodium

phosphate dibasic in water for injection

Shipment and storage: Refrigerated, 2-8 °C

ARO-HSD will be prepared, per the Pharmacy Manual, by a pharmacist or qualified pharmacy staff member at the clinical sites. Aseptic technique will be used to ensure sterility of the solution to be injected. The time of preparation for active drug must be documented and tracked to demonstrate administration within prepared drug stability boundaries. Please refer to the Pharmacy Manual for more detailed instructions.

The investigational product vials will be labelled per Good Manufacturing Practice (cGMP)/Good Clinical Practice (cGCP).

Study drug supplies will be stored at clinical sites securely under the appropriate conditions as noted in the Pharmacy Manual.

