## 10.4 Allocation of Treatment

Participants will receive study drug by assigned cohort (Table 4) as outlined in Section 7.1. Treatments will be administered per the randomized sequence (where applicable) kept by the pharmacy or in a secure place at the clinical site, under control of the un-blinded staff member.

Table 5 Injection Number and Volume per Cohort

Cohort	Dose	Concentration	Total Injection Volume
1, 1b	25 mg	200 mg/mL	0.125 mL
2	50 mg	200 mg/mL	0.25 mL
3, 3b	100 mg	200 mg/mL	0.5 mL
4, 4b	200 mg	200 mg/mL	1 mL

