#### 10.5 Study Treatment Administration

Appropriately trained employees of the clinical site will administer the study treatment. Each dose will be administered as a single subcutaneous injection. The date, time and location of administration will be recorded in the source notes and witnessed by a second person from the clinical facility. The site of injection will be marked and mapped for later observation. The preferred site of injection is the abdomen. Optional additional sites are the upper arms and thighs.

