# 16.2 Local Injection Site Reactions (LISRs)

The following MedDRA Preferred Terms determined by the Sponsor's pharmacovigilance personnel represent the local injection site reaction:

Injection site discomfort	Injection site abscess
Injection site discoloration	Injection site abscess sterile

Injection site erythema	Injection site atrophy
Injection site irritation	Injection site calcification
Injection site inflammation	Injection site cellulitis
Injection site induration	Injection site dermatitis
Injection site pain	Injection site erosion
Injection site oedema	Injection site fibrosis
Injection site pruritus	Injection site indentation
Injection site rash	Injection site necrosis
Injection site urticaria	Injection site nodule
Injection site reaction	Injection site ulcer
Injection site swelling	

LISRs will only include events that start on the day of injection and persist for at least 48 hours post injection (i.e., event onset date on the day of injection and resolution date not on the day of injection or the day after the injection) will be included. Events with onset date on the day of injection and missing resolution date will also be included in the summary.

The following calculation will be utilized to determine the percentage of injections leading to local injection site reactions:

 $(A/B)^*$ , where A = number of injections with a local injection site reactions, and B = total number of injections.

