9.6.1 Adverse Events

Adverse event (AEs) will be coded using the Medical Dictionary for Regulatory Activities (MedDRA, the latest available version) and data will be summarized by System Organ Class (SOC) and a Preferred Term.

A table providing an overall summary of AEs will be produced which will include the number of TEAEs; the number and percentage of participants reporting at least one: TEAE, TESAE, grade 3 (severe) or higher TEAE, TEAE related to study treatment (possibly or probably related to ARO-HSD), TESAE related to study treatment, grade 3 or higher TEAE related to the investigational product and TEAE leading to drug or study withdrawal.

Descriptive statistics summaries of subject incidence will be summarized for all TEAEs, treatment-related TEAEs, TESAEs, treatment-related TESAEs, and TEAEs resulting in investigational product withdrawal or study discontinuation, treatment emergent fatal AEs, TEAE at injection site and TEAE related to LISR will be tabulated by SOC in alphabetical order and PT in descending order of frequency. Descriptive summaries will include count and percent of subjects as well as number of events..

Descriptive statistics summaries of subject incidence of TEAEs, TEAE at injection site and TEAE related to LISR by SOC, PT, and severity will be provided. Subjects will be counted once under the highest severity reported within each SOC and PT. The events will be counted the number of times they occur within each SOC and PT.

Descriptive statistics summaries of subject incidence of TEAEs by SOC, PT, and relationship to investigational product will be provided. Subjects will be counted once under the closest relationship reported within each SOC and PT. Events will be counted the number of times they occur within each SOC and PT.

A by-subject AE data listing, including verbatim term, MedDRA SOC and PT, TEAE flag, seriousness, severity, outcome and relationship to study treatment will be provided. Separate listings will be generated for SAEs.

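### Injection-site and LISR tables: pooling placebo across cohorts hides the study's only control for injected volume, so by-cohort placebo columns should be added beside the pooled one

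*SAP*

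**What the plan says.** **Dosing.** The product has one concentration ("Strength: 200 mg/mL Volume: 1.0 mL", Protocol 9.1), and Protocol 10.5 says "Each dose will be administered as a single subcutaneous injection". Protocol 10.4, Table 5 ("Injection Number and Volume per Cohort") gives 0.125, 0.25, 0.5 and 1 mL for 25, 50, 100 and 200 mg.

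**Placebo.** The synopsis describes saline, "volume matched to the corresponding ARO-HSD dose volume". On allocation it says "Each double-blind cohort will enroll eight (8) subjects (4 active: 4 PBO". Cohorts 1b, 3b and 4b are open label with no placebo.

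**Analysis.** SAP 9.1 presents summaries by treatment unless otherwise noted and adds "Subjects receiving placebo will be pooled across cohorts". SAP 9.6.1 says "TEAE at injection site and TEAE related to LISR will be tabulated by SOC", with a further breakdown by severity, and notes no exception to pooling. Protocol 12.3 says that safety results are in general summarised by cohort and treatment group. SAP section 10 reports no changes from the protocol's analyses.

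**Per-injection rate.** Protocol 16.2 states: "The following calculation will be utilized to determine the percentage of injections leading to local injection site reactions". The SAP cites 16.2 only for its list of preferred terms and does not carry the calculation over.

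**The concern.** Because concentration is fixed, dose and volume cannot be separated within the active arms. The design does contain the means to separate them: within each healthy-volunteer cohort, half the subjects receive the same volume of saline. If volume alone drove local reactions, the rate would rise across cohorts in both arms, and a reader who saw both would recognise the cause.

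Under SAP 9.1 the reader sees four active columns ordered by dose beside one placebo column that averages over all four volumes. Of the 16 planned placebo subjects, only 4 receive 1 mL. A rise in placebo would be averaged out of sight, and the rise in active could be taken for a drug effect. Protocol 5.7 names injection site reactions as a risk, and these events have their own tables.

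**Working it through.** **1. Volumes.** Volume = dose / concentration: 25/200 = 0.125, 50/200 = 0.25, 100/200 = 0.5 and 200/200 = 1.0 mL. This reproduces Table 5. The range is 1.0/0.125 = 8-fold. Pooled placebo n = 4 x 4 = 16.

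**2. Effect of pooling if only volume matters.** The documents give no reaction rates by volume, so the rates here are assumptions. The true drug effect is set to zero, so active and placebo share the same risk in each cohort. Pooled placebo is the mean of the four cohort risks.

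Base case, risk proportional to volume with 20% at 1 mL: pooled placebo = (2.5 + 5 + 10 + 20)/4 = 9.4%.

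| Dose | Volume (mL) | Risk, both arms | Active minus pooled placebo | Active minus own-cohort placebo |
|---|---|---|---|---|
| 25 mg | 0.125 | 2.5% | -6.9 points | 0 |
| 50 mg | 0.25 | 5% | -4.4 points | 0 |
| 100 mg | 0.5 | 10% | +0.6 points | 0 |
| 200 mg | 1.0 | 20% | +10.6 points | 0 |

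Other assumptions, 25 mg to 200 mg:
- Risk linear in volume from 10% to 20%: pooled placebo 13.9%, differences -3.9 to +6.1 points.
- Risk proportional to volume, 40% at 1 mL: pooled placebo 18.75%, differences -13.8 to +21.3 points.
- Flat risk at any level: difference 0 at every dose.

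**3. Precision of the two comparators.** Root mean squared error of the active-minus-placebo difference, with p the risk in the cohort shown and p_j the risk in cohort j:
- Pooled: square root of [bias² + p(1-p)/4 + Σ 4p_j(1-p_j)/16²].
- Own cohort: square root of [2p(1-p)/4].

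At 200 mg, base case: pooled = √(0.10625² + 0.0400 + 0.0050) = 0.237; own cohort = √0.0800 = 0.283. With 40% at 1 mL: pooled = √(0.2125² + 0.0600 + 0.0084) = 0.337; own cohort = √0.1200 = 0.346. With 10% to 20%: pooled = √(0.0607² + 0.0400 + 0.0074) = 0.226; own cohort = 0.283.

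Pooled is therefore more accurate at 200 mg in all three cases, even after its bias is counted. Own-cohort placebo does better only at 25 mg in the two proportional cases (0.110 against 0.126, and 0.154 against 0.198).

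**4. What four subjects can show.** If 0 of 4 react, the one-sided 95% upper limit is 1 - 0.05^(1/4) = 52.7%. For 0 of 16 it is 1 - 0.05^(1/16) = 17.1%.

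**5. Overall comparison.** With 4:4 allocation in every cohort, all-active and all-placebo have the same mean volume, (0.125 + 0.25 + 0.5 + 1)/4 = 0.469 mL. The crude all-active against all-placebo comparison is already balanced for volume, so stratifying it by cohort adds nothing.

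**The case against.** The case for leaving the tables alone is substantial.

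- **No document shows that volume causes these reactions.** Protocol 5.7 links them to modified siRNA products, Protocol 11.5.2 describes an LISR as usually immunologic, and every planned volume is within the approximate 1.0 mL per-site limit in Protocol 9.1. This stands, and it makes the point conditional.
- **Pooling does not create the active gradient.** A reader might infer that pooling manufactures a spurious dose-response. It does not. Any rise across active columns comes from the fixed concentration; pooling only hides the placebo rise that would explain it. The SAP also plans no active-minus-placebo difference and no formal hypothesis test.
- **Pooled placebo is usually the more accurate comparator.** The base-case shift of 10.6 points at 200 mg is less than half a subject when one of four is 25 points. This stands, and it rules out replacing the pooled column.
- **Protocol 9.6 also pools placebo.** That passage covers an interim summary arranged to avoid unblinding, a reason that ends once the cohorts are unblinded. Its adverse-event comparison is pooled active against pooled placebo, which is balanced for volume.
- **The data are not lost.** A by-subject adverse event listing is planned, SAP 3.1 allows cohorts to be summarised individually, and the table shells are in a companion document not available here. This lowers the stakes, but the SAP text governs the tables and makes no exception.

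The departure from Protocol 12.3 should not be pressed too hard either: its sentence is qualified as a general rule.

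**Conclusion.** The point holds in a limited, conditional form. Volume tracks dose exactly, matched placebo is the study's only control for volume, and the SAP's pooling rule reaches the injection-site and LISR tables without an exception and without being declared as a change from Protocol 12.3. If reaction risk depends on volume, the pooled-only display hides a parallel placebo gradient. Under the assumed rates above, the apparent contrast runs from -3.9 to +6.1 points in the mildest case and from -13.8 to +21.3 points in the steepest; under a flat risk it is zero. Cohorts 3 and 4 are capped doses, so a lower dose set by the Data Safety Committee would narrow the volume range.

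The documents do not support the stronger conclusions that the pooled comparison is biased as a matter of fact, or that pooled placebo should be dropped. This is an inexpensive improvement to a descriptive display.

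The missing per-injection LISR percentage is a separate omission. Each healthy volunteer has one injection, so it equals the per-subject percentage there; it can differ only in Cohorts 1b, 3b and 4b, where two doses are planned and there is no placebo. It has no bearing on pooling.

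**What to change.** In SAP 9.1 and 9.6.1, for the injection-site TEAE and LISR tables only:

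1. Show placebo by cohort beside the active dose of the same volume, with the volume in the column header.
2. Keep the pooled placebo column.
3. Add a pooled-active column for Cohorts 1-4 as the volume-balanced overall comparison. No stratified row is needed.
4. State that the by-cohort columns are descriptive.

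If the sponsor prefers pooled placebo alone, record that in SAP section 10 as a change from Protocol 12.3.

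Separately, add the Protocol 16.2 per-injection LISR percentage to SAP 9.6.1.

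The cost is a few lines of SAP text and some extra table columns, with no new data. The drawback is four-subject placebo columns, in which even 0 of 4 is compatible with a true rate of up to about 53% (one-sided 95% limit).
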